 - ⑤ Start date of administration,
- 3) In case any patient who had been administered with LipaCreon were enrolled, the information before the enrollment is to be collected as much as possible if it is required in the registry items.

(3) Observation Period

The observation period for a case is at least 52 weeks from the start of administration of LipaCreon. Even if the administration period exceeded 52 weeks, the assessment is to be done at the time of 52nd weeks. After 52nd week, administration status, concomitant use drug status, nutritious assessment items, symptoms relating to pancreatic excretion insufficiency and adverse events should be described in the Follow-up Case Report Form, and it should be submitted to the sponsor company.

(4) Description and submission of the Case Report Form

In this Registry, the Case Report Form is consisted of seven report brochures. After each whole follow-up period per case is completed, follow-up items should be fulfilled on all the registered cases (incl. discontinued cases). After all items were fulfilled, final confirmation date

should be written, signature should be done, and seal should be done before submission.

The Case Report Form (1): From the first administration date to 52nd week

The Case Report Form (2) – (7): After 52nd administration, one CRF per year

(5) Discontinued cases

In this Registry, the cases which the administration was discontinued during the observation period, or which follow-up became impossible due to patient's visit stopped, or other reasons, will be handled as "discontinued cases". For these discontinued cases, stopped date, reason of stopping, assessment done until the discontinuation should be written in the forms.

7. Planned registry period

Planned registry period: From the release of Lipa Creon to 31st March 2018

Case registration period: From the release of Lipa Creon to 31st March 2017

Observation period: For 52 weeks from the start of administration of LipaCreon. Even if the administration period exceeded 52 weeks, the assessment is to be done at the time of 52nd weeks.

Follow-up period: After the 52nd week, administration status, concomitant use drug status, nutritious assessment items, symptoms relating to pancreatic excretion insufficiency and adverse events should be described in the Follow-up Case Report Form annually, and it should be submitted to the company.

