After administration of LipaCreon started, the information will be collected until the end of March 2018. First 52 weeks from the start will be observation period and 53 weeks and onwards will be follow-up period.

8. Survey items

(1) Items required for specifying the patient:

Patient ID No.

(2) Patient background:

Sex, presence or absence of pregnancy/breast feeding (female only), date of birth or age, inpatient/outpatient classification, start date of administration, concomitant diseases (hepatic, renal or respiratory disorders, other), history of disease, history of allergy, prior treatment drug (digestive enzyme product)

(3) Administration status of LipaCreon:

Daily dose, administration period, drug regimen compliance, the reason for a change in dose

(4) Administration status of concomitant drugs:

[Other digestive enzyme products]:

Presence or absence of treatment with other digestive enzyme product, drug name, daily dose, administration period

[Other concomitant drugs]:

When additional information is required at the onset of adverse event, etc., the following information is investigated:

Presence or absence of information for the concomitant drugs, drug name, administration route, reason for use, daily dose, administration period

(5) Adverse events

All the undesirable or unintended diseases, or their symptoms, signs or abnormal changes in laboratory test values, etc. that have occurred in the patients administered LipaCreon are handled as the adverse events regardless of the causal relation to LipaCreon. The adverse events whose causal relation to LipaCreon is not deniable are handled as adverse reactions.

Concerning the adverse events that occur from the start to the completion of administration of LipaCreon, the following items are investigated. In principle, the course of adverse event is observed until the event is judged by the physician in charge of registry to cause no clinical problem.

Diseases, symptoms, signs or abnormal changes in laboratory test values which were attributed to the cystic fibrosis, will not be regarded as adverse event, but as the events attributed to cystic fibrosis.(please refer to [(6) Events attributed to cystic fibrosis])

1) Presence or absence of adverse event 2) Name of adverse event

3) Date of onset 4) Seriousness 5) Administration of LipaCreon

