6) Measure taken about the adverse event 7) Date of outcome (or outcome confirmation date) 8) Outcome 9) Causal relation to LipaCreon 10) Factors other than LipaCreon 11) Symptoms and history of adverse event 12) Laboratory test results related to the adverse event 13) Comment on the adverse event

(6) Events attributed to cystic fibrosis

Information regarding below items should be collected on the diseases, symptoms, signs or abnormal changes in laboratory test values which were attributed to the cystic fibrosis occurred after administration of LipaCreon.

- 1) Presence or absence of event attributed to cystic fibrosis
- 2) Name of event
- 3) Date of onset 4) Measure taken about the event
- 5) Date of outcome (or outcome confirmation date)
- 6) Outcome

(7) Nutrition assessment items

The following nutrition assessment items are determined before the start and after 4, 8 and 24 weeks from the start of administration of LipaCreon, at the end of observation period or at the time of discontinuation during observation period, and per year or at the end of follow-up period or at the time of discontinuation during follow-up period.

If the dosage increase from usual dosage (1800mg/day) is to be done during the observation period or follow-up period, perform assessment before the dosage increase.

- BMI (Height, body weight)
- Serum total protein
- Albumin
- Total cholesterol
- Triglyceride
- Hemoglobin

(8) Symptoms relating to pancreatic exocrine insufficiency

Following symptoms should be monitored at the timing before the start of administration, 4th, 8th, 24th week after administration started, and completion/discontinuation of follow-up during the observation period,

and per year or at the end of follow-up period or at the time of discontinuation during follow-up period. If the dosage increase from usual dosage (1800mg/day) is to be done during the observation period or follow-up period, those symptoms should be monitored before the increase will take place.

- Steatorrhea
- Frequency of defecation
- Diarrhea
- Bad odor of feces
- Appetite loss
- Abdominal distention

(9) Overall improvement rating

The overall improvement is assessed in the following 4 grades after 24 weeks from the start of administration of LipaCreon, and at the end of observation period at 52nd week or at the time of discontinuation.

Effective, unchanged, aggravation, unassessable

(10) Discontinuation

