When the administration is discontinued during the observation period, or when follow-up became impossible due to patient's visit stopped, or other reasons, the date of discontinuation and the reason for discontinuation is stated in the CRFs.

(11) Case of pregnancy

The information related to pregnancy is separately investigated in the pregnant case and the case whose pregnancy is found during the observation period at the point the pregnancy is known and after the birth of baby.

Survey schedule

Survey items	At the start of administration	Time point					
		During observation period				During Follow-up period	
		After 4 weeks	After 8 weeks	After 24 weeks	After 52 weeks or at the discontinuation	Per year	At the end of Follow-up Period (Mar. '18) or at the discontinuation
Registration	○						
Patient background	○						
Administration status of LipaCreon	○			○		○	○
Administration status of concomitant drug	○			○		○	○
Nutrition assessment items*	○	○	○	○	○	○	○
Symptoms relating to pancreatic exocrine insufficiency *	○	○	○	○	○	○	○
Overall improvement rating				○	○		
Reason for discontinuation					At the time of discontinuation ○		At the time of discontinuation ○
Adverse events	Investigation from the start of administration and throughout the observation period						
Events attributed to cystic fibrosis	Investigation from the start of administration and throughout the observation period						

* : If dosage increase from usual daily dosage (1800mg) is to be done during the observation period or follow-up period, perform measurement of nutritious assessment items and monitor the symptoms relating to pancreatic exocrine insufficiency before the dosage increase.

9. Timing, items and methods of analysis

(1) Timing of analysis

After 3 or 4 years from start of registry, the interim analysis is to be done.

And at the end of registry, the final analysis is to be done.

(2) Matters related to case formation

- Number of registered cases and number of cases from which the CRF is collected
- Number of cases accepted for safety and efficacy analysis
- Number of cases excluded from analysis and the reason for exclusion

(3) Matters related to safety

- Adverse reaction onset status
- Factors considered to have influence on the safety (The incidence of ADRs by patient background)
- Adverse event and serious adverse event

(4) Matters related to effectiveness

- Changes in nutrition assessment items
- Overall improvement rating

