4.5.1.1. Occurrence of events associated with cystic fibrosis of the pancreas

For patients included in the safety analysis, a list of reported events associated with cystic fibrosis of the pancreas will be prepared (Table 5.1.1).

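### The protocol is inconsistent on whether events attributed to cystic fibrosis are collected after Week 52, and the SAP tabulates them without stating a window

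*Protocol*

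**What the plan says.** Five places in the protocol bear on this.

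- **8(5), Adverse events.** Anything attributed to CF "will not be regarded as adverse event, but as the events attributed to cystic fibrosis". The rule has no time limit and refers the reader to 8(6).
- **8(6), Events attributed to cystic fibrosis.** Information is to be collected on events "which were attributed to the cystic fibrosis occurred after administration of LipaCreon". No end point, form or visit is named.
- **Section 8, Survey schedule.** The row for CF-attributed events reads "Investigation from the start of administration and throughout the observation period". The adverse-event row has the same words.
- **Section 7, Planned registry period.** "First 52 weeks from the start will be observation period and 53 weeks and onwards will be follow-up period".
- **6(3) and 7, content of the yearly follow-up forms.** Section 7 ends its list with "symptoms relating to pancreatic excretion insufficiency and adverse events should be described in the Follow-up Case Report Form annually"; 6(3) gives the same items. Neither list includes CF-attributed events.

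In the SAP, 4.5.1.1 says that for the safety set "a list of reported events associated with cystic fibrosis of the pancreas will be prepared (Table 5.1.1"), without a period. Table 5.2.1.1 (SAP 4.5.2.1) shows for each patient whether such events were present or absent, also without a period.

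**The concern.** In this registry the attribution to CF decides where an event is written down. Once the physician makes it, the event leaves the adverse-event item, and 8(6) is the only event item left. Whether 8(6) applies after Week 52 therefore decides whether the event is on record at all, and the protocol gives two answers.

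What is at stake is the long-term safety record. The SAP tabulates adverse-event onset out to 2400 days (4.2.1.2), so long-term safety is plainly intended. Protocol section 4 warns of bowel stenosis reported in CF patients on high-dose pancreatin products and asks for careful observation of abdominal changes. A bowel event in such a patient could plausibly be put down to CF. If it is recorded as a CF event, the attribution can be re-examined later; if not, it cannot. If sites read the protocol differently, an entry of absent in Table 5.2.1.1 may mean that no event occurred, or that nobody asked after the first year.

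**Working it through.** The documents give no figure to reproduce, so the first check is a comparison of the text.

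| Source | CF-attributed events to Week 52 | After Week 52 |
|---|---|---|
| 8(6) | collected | collected (no end stated) |
| Survey schedule row | collected | not covered, if observation period has its section 7 meaning |
| Follow-up form lists, 6(3) and 7 | not applicable | not listed |
| 8(5), adverse-event item | excluded | excluded |

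On the second and third rows, an event after Week 52 attributed to CF has no event item to go into. On the first row it has one. The protocol does not say which source prevails. Where it wants follow-up data on a survey item, it elsewhere says so: 8(7) and 8(8) spell out yearly and end-of-follow-up assessments. 8(6) does not.

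The second check is how much patient-time depends on the answer.

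*Inputs.* Survey period 30 August 2011 to 31 March 2018 (SAP 1.2). Last registration 31 March 2017 (Protocol 7). Days = end − start + 1, and 52 weeks = 364 days (SAP 3.5).

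*Assumptions, not in the documents.* Treatment starts are uniform between 30 August 2011 and 31 March 2017; patients stop at a constant rate, 0% to 30% per 364 days.

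*Range of follow-up.*
- Start 30 August 2011: 2406 days, of which 2406 − 364 = 2042 (84.9%) fall after Day 364.
- Start 31 March 2017: 366 days, of which 2 (0.5%) fall after Day 364.

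*No stopping.* Mean follow-up = (366 + 2406)/2 = 1386 days. Share after Day 364 = (1386 − 364)/1386 = 1022/1386 = 73.7%.

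*With stopping.* For a fraction p stopping per 364 days, the daily rate is λ = −ln(1 − p)/364. Mean time on treatment is the average of (1 − e^(−λT))/λ over T = 366 to 2406 days. The part up to Day 364 is (1 − e^(−364λ))/λ.

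| Stopping per 364 days | Mean days on treatment | Up to Day 364 | After Day 364 |
|---|---|---|---|
| 0% | 1386 | 364 | 73.7% |
| 10% | 1108 | 345 | 68.8% |
| 20% | 887 | 326 | 63.2% |
| 30% | 712 | 306 | 57.0% |

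These are shares of patient-time, not of events. No event rate is given, and the number of sites following each reading is unknown.

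**The case against.** The best defence is that 8(5) and 8(6) work as a pair. The first does not discard CF-attributed events but passes them to the second; neither has a time limit, and section 7 says information is collected until the end of March 2018. On that reading there is no gap.

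The schedule row is also weak evidence by itself. The adverse-event row has the same words, yet 6(3), 7 and 8(5) clearly carry adverse events into follow-up, so the phrase may be loose. 6(3) adds to this: "The observation period for a case is at least 52 weeks from the start of administration of LipaCreon".

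The case report form, which would settle the matter, is listed as an attachment but is not in the documents. SAP Table 5.2.1.3, though headed adverse events, has fields close to those of 8(6) and a column for the form volume. That is compatible with collecting CF events in follow-up, without proving it. Some CF-related change is captured after Week 52 in any case: nutrition items and pancreatic symptoms are assessed yearly, and worsening of CF is a listed reason for discontinuation.

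Much of this stands. It rules out treating the loss as established, and it means the schedule row cannot carry the point alone. What it does not answer is the omission from both follow-up lists. For adverse events those lists correct the loose schedule wording; for CF-attributed events nothing does. The yearly assessments are status checks on named items and would not record, for example, a hepatic or respiratory event.

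A reader might infer that CF-attributed events after Week 52 are certainly lost, that Table 5.1.1 would hold only 26% to 43% of them (100% less the 74% and 57% above), and that they would appear to fall off after the first year. The documents do not support this. The percentages need zero capture after Week 52, which is the disputed point, and a constant event rate. No SAP table shows CF events over time, so there is no trend to distort.

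**Conclusion.** The inconsistency is real and should be resolved. Under the schedule and the follow-up lists, a CF-attributed event after Week 52 is recorded neither as an adverse event nor as a CF event; under 8(6) it is recorded. Sites could act on either reading, and the two SAP outputs would then combine them with no stated window.

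About 57% to 74% of patient-time is exposed, given uniform entry and 30% to 0% stopping per year. The loss within that time runs from none, if 8(6) is followed everywhere, to all CF-attributed events, if the schedule and lists are followed everywhere. The documents do not show where in that range the registry lies.

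**What to change.** - In Protocol 6(3) and 7, add CF-attributed events, with the items in 8(6), to the content of the follow-up forms.
- In the survey schedule, extend the row for CF-attributed events to cover both the observation and the follow-up period. Change the adverse-event row to match.
- In SAP 4.5.1.1, state the collection window of Table 5.1.1 and show events up to and after Day 364 separately. State the same window for the flag in Table 5.2.1.1.
- Check the follow-up forms in use. Only if they lacked an item for CF-attributed events, query the follow-up volumes already collected.

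The cost is a wording change in both documents and a few more entries per yearly form. Any querying should be limited: Protocol section 2 cites 38 CF patients nationwide over ten years.

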Attachment

- (a) Agreement for PMS
- (b) Outline for Special Investigation
- (c) Registration form for Special Investigation
- (d) Case report form for Special Investigation

1.1. Purpose of the Survey

This survey will be conducted to collect information on the safety and effectiveness of Lipacreon in patients with exocrine pancreatic insufficiency due to cystic fibrosis of the pancreas, thereby obtaining information to use Lipacreon effectively and safely.

1.2. Outline of the Survey

Brand name: Lipacreon® Granules 300 mg Sachets, Lipacreon® Capsules 150 mg

Survey name: Special Drug Use-Results Survey

CF all-case surveillance: P12-893/LPC02T

Special Drug Use-Results Survey (all-case surveillance) —All-Case Surveillance in Patients with Exocrine Pancreatic Insufficiency due to Cystic Fibrosis of the Pancreas—

Date of approval: April 22, 2011

Date of designation: April 14, 2011

End date of the re-examination period: April 21, 2019

Survey period: August 30, 2011 through March 31, 2018

1.3. Drug Product and its Dosage and Administration

Lipacreon® Granules 300 mg Sachets

Each sachet contains 300 mg of pancrelipase.

Lipacreon® Capsules 150 mg

Each capsule contains 150 mg of pancrelipase.

The usual dosage is 600 mg/dose of pancrelipase administered orally immediately after each meal three times daily. The dosage may be adjusted according to the condition of the patient.

1.4. Target Disease

Patients with exocrine pancreatic insufficiency due to underlying cystic fibrosis of the pancreas

2. Definitions of Terms and Abbreviations

2.1. Definitions of Analysis Sets

No	Definition name	Description
1	Survey period	
Reporting interval for periodic safety reports
 
3rd: April 14, 2012 to October 13, 2012
 
4th: October 14, 2012 to April 13, 2013
 
5th: April 14, 2013 to April 13, 2014
 
6th: April 14, 2014 to April 13, 2015
 
7th: April 14, 2015 to April 13, 2016
 
8th: April 14, 2016 to April 13, 2017
 
9th: April 14, 2017 to April 13, 2018
 
10th: April 14, 2018 to April 13, 2019
 
End date of the re-examination period
 
April 21, 2019

2	Data lock dates	
The data lock date for periodic safety reports are as follows:
 
3rd: October 13, 2012
 
4th: April 13, 2013
 
5th: April 13, 2014
 
6th: April 13, 2015
 
7th: April 13, 2016
 
8th: April 13, 2017
 
9th: April 13, 2018
 
10th: April 17, 2019
 
The data lock date for re-examination is as follows:
 
April 17, 2019
 
At each analysis, the following case report forms will be analyzed:
 
Periodic safety report: Case report forms whose case report form status on each data lock date is “Primary data lock”
 
Analysis for re-examination: All case report forms whose case report form status is “Data lock”

3	Patients registered in the survey	Patients who have been able to be registered in the survey
4	Patients with available case report forms	Patients whose case report forms have been collected
5	Patients with no available case report forms	Patients whose case report forms have not been able to be collected
6	Criteria for exclusion from the safety analysis	
 ▪ No dose received: Patients whose use of Lipacreon has not been able to be confirmed ▪ No visit made: Patients who have not visited the institution since the start date of treatment with Lipacreon
7	Patients excluded from the safety analysis	Patients meeting the criteria for exclusion from the safety analysis among the patients with available case report forms
8	Patients included in the safety analysis	Patients not meeting the criteria for exclusion from the safety analysis among the patients with available case report forms
9	Criteria for exclusion from the effectiveness analysis	
 ▪ Cannot be determined: Patients in whom all of “nutritional endpoints, symptoms related to exocrine pancreatic insufficiency, and degree of overall improvement” after the start date of treatment are unknown/unspecified or cannot be determined
10	Patients excluded from the effectiveness analysis	Patients meeting the criteria for exclusion from the effectiveness analysis among the patients included in the safety analysis

No	Definition name	Description
11	Patients included in the effectiveness analysis	Patients not meeting the criteria for exclusion from the effectiveness analysis among the patients included in the safety analysis
12	Patients not completing the 52-week treatment	Patients who have discontinued treatment before Week 48 among the patients included in the effectiveness analysis
13	Patients included in the effectiveness analysis (patients completing the 52-week treatment)	Patients who have completed the 52-week treatment among the patients included in the effectiveness analysis

LPC02T will target all patients, even those who have transferred to another department or hospital. If the same patient is registered multiple times at different institutions or departments, overlapped registrations will be linked to each other and counted as “1 patient.” All case report forms/follow-up case report forms collected at the individual departments/institutions will be regarded as separate volumes for the same patient and the data included in the case report forms will be handled accordingly. Evaluation time points will be calculated with the first “start date of treatment” being deemed as the starting point.

Details will be determined depending on the actual case.

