4.1.1.3. Breakdown of patient composition

The following will be presented: the number of institutions surveyed, the number of patients registered in the survey, the number of patients with available case report forms, the number of patients with no available case report forms, the number of patients included in the safety analysis, the number of patients excluded from the safety analysis, the number of patients included in the effectiveness analysis, the number of patients excluded from the effectiveness analysis, the number of patients included in the effectiveness analysis (patients completing the 52-week treatment), and the number of patients not completing the 52-week treatment. For patients excluded from the safety analysis and patients excluded from the effectiveness analysis, the number of the individual patients will be presented by reason for exclusion (Figure 1.1.3.1).

In addition, the number of patients with available case report forms will be presented by separate volume (Figure 1.1.3.2).

For patients with multiple reasons for exclusion among the patients excluded from the safety analysis or patients excluded from the effectiveness analysis, a list of patients will be prepared (Table 1.1.3.1, Table 1.1.3.2).

For patients excluded from the safety analysis, lists of reported adverse events will be prepared by SOC, PT, seriousness, and presence/absence of relationship (Table 1.1.3.3).

For discontinued patients, a list of patients will be prepared by survey-participating institution (Table 1.1.3.4).

No	Item name	Contents to be displayed
1	Survey-participating institution	-
2	Department name	-
3	Patient number	-
4	Age	Actual value
5	Sex	Male, female
6	Start date of treatment	-
7	End date of treatment	-
8	Number of days from the start of treatment to discontinuation	-
9	Reason for discontinuation	Occurrence of an adverse event, unsatisfactory therapeutic effect, patient's refusal to receive Lipacreon, no visit, worsening of cystic fibrosis of the pancreas, other For "other," a specific reason for discontinuation will be presented.
10	Name of the adverse event as the reason for discontinuation	-
11	Seriousness	Non-serious, serious
12	Causal relationship with Lipacreon	Related, possibly related, unrelated, cannot be determined
13	Outcome	Resolved, resolving, not resolved, sequelae, fatal, unknown
14	Date of onset	-
15	Number of days to onset	-
16	Inclusion/exclusion of patient in the safety analysis	Included, excluded

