4.2.1.1. Occurrence status of adverse events

For patients included in the safety analysis, the number of patients with adverse events, the percentage of patients with adverse events (with the number of patients included in the safety analysis being the denominator), and the number of reported adverse events will be calculated by SOC, PT, seriousness, and causal relationship with Lipacreon (Table 2.1.1.1). The number of patients with adverse events and the number of reported adverse events will be counted as described in Section 3.4. In addition, seriousness and causal relationship with Lipacreon by patient will be determined first for “Serious” events and “Related” events.

The breakdown of patients with serious events will be calculated (Table 2.1.1.2).

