4.6. Attached Forms

4.6.1. Attached forms

- Patients for summarization: Patients with available case report forms

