4.6.1.1. List of reported adverse drug reactions and infections [Attached Form 2]

The occurrence of adverse drug reactions and infections will be summarized.

Line

No	Item name	Description
1	Number of institutions surveyed	The same institution name will be regarded as 1 institution.
2	Number of patients surveyed	The separate volume for each reporting interval will be counted as the number of patients. If only 1 separate volume is locked, 1 separate volume will be regarded as 1 patient. If 2 separate volumes are locked at the same time, 2 separate volumes will be regarded as 1 patient. The total number of patients surveyed will be counted as the number of patients irrespective of separate volumes.
3	Number of patients with adverse drug reactions and number of adverse drug reactions	Adverse drug reactions corresponding to the number of patients surveyed (or each reporting interval) will be counted as the number of patients. If the same adverse drug reaction (PT) occurs repeatedly and is recorded multiple times, the adverse drug reaction will be summarized in the row of the period in which the firstly completed separate volume is counted. In addition, adverse drug reactions corresponding to the number of patients surveyed (total) will be counted as the number of patients.
4	Percentage of patients with adverse drug reactions	= Number of patients with adverse drug reactions / number of patients included in the safety analysis × 100
5	System organ class	MedDRA SOCs will be used. If the same patient experiences any adverse drug reaction (MedDRA SOC) multiple times, the patient will be counted once. Adverse drug reactions will be displayed in the SOC internationally agreed order.
6	Event name	MedDRA PTs will be used. If the same patient experiences any adverse drug reaction (MedDRA PT) multiple times, each event will be counted once. Adverse drug reactions will be displayed in the order of PT codes.

Row

No	Item name	Description
1	Survey period	See Section 2.1.

An unknown adverse drug reaction will be displayed with an asterisk (*) on its left side.

Novelty information (unknown or known) will be included in the information on MedDRA coding information provided by Mylan EPD G.K. Based on the novelty information, it will be determined whether an adverse drug reaction is unknown or not.

4.6.1.2. List of reported serious adverse events [Periodic safety report, Attached Form 2-2; Re-examination, Attached Form 10]

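### The SAP's 'No visit made' rule can remove a treated patient with a reported adverse event from the main safety incidences

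*SAP*

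**What the plan says.** SAP 2.1 No. 6 gives two reasons for leaving the safety analysis. The first is unconfirmed use: "No dose received: Patients whose use of Lipacreon has not been able to be confirmed". The second is non-attendance: "No visit made: Patients who have not visited the institution since the start date of treatment with Lipacreon". No. 8 defines the safety set as the remainder: "Patients not meeting the criteria for exclusion from the safety analysis among the patients with available case report forms".

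The outputs then use different populations:

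- **SAP 4.2.1 to 4.2.3** (adverse events, adverse drug reactions, serious events, onset, outcome, risk factors) use the safety set. The main table gives percentages "with the number of patients included in the safety analysis being the denominator".
- **SAP 4.7.1.1 and 4.7.1.2** (new-notification Attached Forms 2 and 15) count reactions in the safety set.
- **SAP 4.6.1** (Attached Forms 2 and 2-2) has a wider population: "Patients for summarization: Patients with available case report forms". Its percentage in 4.6.1.1 is nevertheless "Number of patients with adverse drug reactions / number of patients included in the safety analysis × 100".
- **SAP 4.1.1.3** provides Table 1.1.3.3: "For patients excluded from the safety analysis, lists of reported adverse events will be prepared by SOC, PT, seriousness, and presence/absence of relationship". It covers both exclusion reasons together and gives no rate.

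The protocol, section 8(5), asks for adverse events from the start to the completion of administration and sets no condition that the patient attended. Section 6(5) treats patients whose visits stopped as discontinued cases, with data recorded up to that point.

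**The concern.** The criterion asks whether the patient came back, not whether anything is known about the patient's safety. A treated patient who dies, or who stops because of a reaction and reports it by telephone or through a physician outside the survey, meets the criterion as written. Failure to return can itself be a consequence of an early reaction, so the exclusion may depend on the outcome being measured.

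This matters because the survey exists to collect safety information on every treated patient in a very rare disease. With so few patients, one case can decide whether a table shows a reaction at all. The SAP also uses an information-based rule elsewhere: under 2.1 No. 9 a patient leaves the effectiveness analysis only when all effectiveness items after the start are unknown or cannot be determined. No reason is given for making the safety criterion depend on attendance.

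**Working it through.** The documents state no incidence or sample size for this point, so there is no figure to reproduce. The check has two parts.

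**1. Where the event goes.** Take a patient with a case report form, confirmed use, no visit after the start date, and one reported adverse drug reaction.

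| Output | Event in numerator? | Patient in denominator? |
|---|---|---|
| SAP 4.2 tables | No | No |
| New-notification Attached Forms 2 and 15 | No | No |
| Attached Forms 2 and 2-2, read literally | Possibly (population is all patients with forms) | No |
| Table 1.1.3.3 | Listed, no rate | – |
| Tables 5.2.1.1 and 5.2.1.3 (patients with forms) | Flagged and listed, no rate | – |

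SAP 4.4.1.1 points the same way. For no-visit patients Table 4.1.1 shows treatment start and end dates and the reason for and date of discontinuation; for patients with unconfirmed use it shows only a registration number. So the SAP treats no-visit patients as people who may have been treated and about whom something may be known.

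**2. Size, as an illustration.** Inputs: N = 38 or 13 patients with forms (protocol section 2: the ten-year total from 1995 and the 2004 count, both nationwide), one excluded patient with an event, and b other patients with an event. Under the SAP the 4.2 incidence is b/(N − 1); with the patient kept it is (b + 1)/N. Read literally, Attached Form 2 gives (b + 1)/(N − 1). Intervals are exact (Clopper-Pearson) 95%; they are added here and the SAP does not plan them.

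| N | b | SAP 4.2 | Patient kept | Attached Form 2, literal |
|---|---|---|---|---|
| 38 | 0 | 0/37 = 0% (0 to 9.5%) | 1/38 = 2.6% (0.1 to 13.8%) | 1/37 = 2.7% |
| 38 | 3 | 3/37 = 8.1% | 4/38 = 10.5% | 4/37 = 10.8% |
| 13 | 0 | 0/12 = 0% (0 to 26.5%) | 1/13 = 7.7% (0.2 to 36.0%) | 1/12 = 8.3% |
| 13 | 3 | 3/12 = 25.0% | 4/13 = 30.8% | 4/12 = 33.3% |

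The 4.2 incidence falls by 2.4 to 2.6 percentage points at N = 38 and by 5.8 to 7.7 points at N = 13.

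**Direction.** Suppose m no-visit patients are excluded, of whom k have a reported event. Exclusion lowers the incidence only if b/(N − m) < (b + k)/N, which is the same as k/m > b/(N − m). With N = 38, m = 3, b = 3 and k = 0, exclusion raises it: 3/35 = 8.6% against 3/38 = 7.9%. With k = 1 it lowers it: 3/35 = 8.6% against 4/38 = 10.5%.

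**The case against.** The strongest case on the other side is that these events are not hidden. Besides Table 1.1.3.3, Table 1.1.3.4 lists each discontinued patient with any event that caused discontinuation, its seriousness, causality and outcome, and whether the patient is in the safety set. With so few patients, individual listings carry much of the safety information. This stands, but a listing does not put the case back into an incidence.

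SAP 2.1 also links registrations when a patient transfers between departments or hospitals and leaves details to the actual case. That removes some situations, but not events learned of outside participating institutions.

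Three stronger readings are tempting, and the documents support none of them:

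- A reader might infer that such events drop out of every incidence. Attached Forms 2 and 2-2, the only forms in the periodic safety reports (SAP 5.2), start from all patients with case report forms, so their numerator may include the event.
- A reader might take Table 1.1.3.3 as proof that the SAP expects events in no-visit patients. It covers both exclusion reasons, so it shows only that events in excluded patients are provided for.
- A reader might conclude that incidences are biased downward. Dropping no-visit patients without events raises the incidence, and the documents give neither count.

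Finally, 13 and 38 are background counts. The protocol plans all cases and sets no number.

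**Conclusion.** The point holds as a defect in a stated rule. As written, SAP 2.1 No. 6 can take a known reaction in a confirmed user out of the section 4.2 incidences and the new-notification Attached Forms 2 and 15. The same reaction could be counted in Attached Form 2 over a denominator that omits the patient, so two re-examination outputs could disagree.

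The shift of one patient is 2.4 to 2.6 points at 38 patients or 5.8 to 7.7 points at 13. This rests on assumed sizes, one such patient, and zero to three other affected patients. The frequency of such cases and the net bias are unknown. The change is worth making because it is cheap and because, in a survey this small, one case can separate a zero from a non-zero incidence.

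**What to change.** **SAP 2.1 No. 6.** Limit 'No visit made' to patients who have not attended since the start date and for whom no safety information after the start (adverse event, outcome or survival status, from any source) was obtained. Confirmed users with any such information then stay in the safety set. Among excluded patients, Table 1.1.3.3 would then hold events only from those whose use could not be confirmed.

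**SAP 4.6.1.** Use the same population for numerator and denominator in Attached Forms 2 and 2-2. The first change does not settle this alone, because patients with unconfirmed use would still be in the wider population but not in the denominator.

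**Reporting.** State how many no-visit patients were kept and how many excluded.

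**Cost.** One clause and one population statement, with no new data. The downside is that a no-visit patient may be kept because an event was reported, while one about whom nothing is known still leaves, which can slightly raise the incidence. With 38 patients, three other affected patients, and three no-visit patients of whom one has an event and two have no information, the new rule gives 4/36 = 11.1%, against 4/38 = 10.5% if all three were kept and 3/35 = 8.6% under the present rule. The reported counts would let a reader judge this.
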